2.5. Sequence of Planned Analyses

2.5.1. Planned Interim Analyses

There will be no formal interim analysis for this study.

2.5.2. Final Analyses and Reporting

All analyses identified in this SAP will be performed after the end of study as defined in the study protocol.

This SAP and any corresponding amendments will be approved before database lock, in accordance to SOP GBP_RD_702 (SAP).

3. ANALYSIS SETS

3.1.1. Intent-to-Treat Analysis Set

The intent-to-treat (ITT) analysis set will include all randomized patients. In the ITT analysis set, treatment will be assigned based on the treatment to which patients were randomized, regardless of which treatment they actually received. This analysis population will be used for summarization of patient disposition and demographic and baseline characteristics, as appropriate.

3.1.2. Modified Intent-to-Treat Analysis Set

The modified intent-to-treat (mITT) analysis set is a subset of the ITT analysis set including only patients who receive at least 1 dose of IMP (IMP is either FS eMDPI or Albuterol eMDPI for the DS group or SoC medication for the SoC group) and at least 1 postbaseline ACT assessment.

In the mITT analysis set, treatment will be assigned based on the treatment to which patients were randomized, regardless of which treatment they actually received. This analysis set will be used for all primary, secondary, [REDACTED] endpoint analyses.

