All patients will have a screening/baseline visit (Visit 1), at which they will be asked if they own a smart device and use different applications on their smartphones. A baseline ACT score for all patients, and BMQ, BIPQ, Mini-AQLQ, and WPAI questionnaire responses for patients 18 years of age or older will be collected. At Visit 1, patients in the DS group will be trained on the use of the eMDPI (including instructions on how to use both the eMDPIs and the App). Upon demonstrating competency, patients in the DS group will have their maintenance ICS with LABA switched to the FS eMDPI (at a dose of fluticasone comparable to their most recent current ICS dose) and their rescue treatment switched to the Albuterol eMDPI. All other asthma maintenance medications, except for ICS with LABA, may be continued. The iHCP can add

37

another controller medication other than an ICS with LABA, including a biologic, to the DS patient's treatment, if needed. Patients in the SoC group will be reimbursed or given a voucher to use to purchase their existing maintenance ICS with LABA and rescue medications. Patients in the DS group will receive a new FS eMDPI device at Visit 1 and 1 FS eMDPI device and 1 Albuterol eMDPI device at Visit 2. Periodically after Visits 1 and 2, patients will be shipped a new FS eMDPI device, which they will need to pair with the App. The patient will immediately stop using the old device and switch to the new device. Extra Albuterol eMDPI devices may be shipped as needed, based on the clinical judgment of the investigator. Upon receipt, the patient will pair the new device with the App and will immediately stop using the old device and switch to the new device. To trigger direct-to-patient (DTP) shipments, after Visit 1, the investigational center will receive periodic email reminders to access the interactive response technology (IRT) system to confirm the dose of test IMP to be shipped to the patient. Confirmation of the dose is required before the next shipment can be sent.

Investigational centers will receive similar instruction regarding features of the App, as well as features of the associated common dashboard, which mirrors the digital information obtained from the eMDPIs and App, including frequency and times of SABA rescue use and associated inspiratory flow parameters measured by the eMDPI with each inhalation.

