4.1. Patient Inclusion Criteria

Patients may be randomized/enrolled in this study only if they meet all of the following criteria:

- a. The patient is 13 years or older at the time of screening.
- b. The patient has a documented diagnosis of asthma established at the investigational center at the time of informed consent or the investigator confirms a diagnosis of asthma.
- c. The patient is currently on treatment with a moderate- to high-dose ICS with LABA.
- d. The patient has an ACT score of less than 19 at the screening or baseline visit.
- e. The patient is willing to discontinue all other maintenance ICS with LABA medications and rescue medications and replace them with the study-provided FS eMDPI and Albuterol eMDPI, respectively, for the duration of the trial, if randomized to the DS group. All other asthma maintenance medications, except for ICS with LABA, may be continued.
- f. The patient can read and communicate in English and is familiar with and is willing to use his/her own smart device that meets the minimum App requirements and download and use the App.
- g. The patient is able to provide written informed consent.
- h. The patient must be willing and able to comply with study requirements and restrictions and to remain at the investigational center for the required duration during the study period, and willing to return to the investigational center for the follow-up procedures and assessments as specified in this protocol.

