3.1.3. Safety Analysis Set

The safety analysis set will include all patients in the DS group who receive at least 1 dose of IMP and all patients in the SoC group. In the safety analysis set, treatment will be assigned based on the treatment patients actually received, regardless of the treatment to which they were randomized, unless otherwise specified. This analysis set will be used for all safety analyses.

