5.2. Patient Disposition

Patients screened and screened but not randomized (with reason not randomized) will be summarized only for all patients using patient counts. Patients in the ITT analysis set, ITT analysis set who did not attempt to download the App, ITT analysis set who did not use the inhaler, safety analysis set, and mITT analysis set, patients who completed and withdrew from treatment (with reason for withdrawing), and patients who completed and withdrew from the study (with reason for withdrawal) will be summarized using descriptive statistics. The summary will be based on all patients. The denominator for calculating the percentages will be the number of patients in the ITT analysis set.

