6. DATA ANALYSIS

6.1. General

The efficacy of the drug product will not be evaluated in this study. The focus of this study is the engagement of the patient with the FS eMDPI DS and Albuterol eMDPI DS.

The mITT analysis sets will be used for all data analyses, unless otherwise specified. Summaries will be presented by treatment group, as randomized.

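### The one-dose condition for the primary analysis set covers both arms on paper but in practice can remove only DS patients, so a DS patient who never inhales leaves the primary analysis unscored

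*SAP*

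**What the plan says.** SAP 3.1.2 defines mITT by two conditions. The first is a dose: "only patients who receive at least 1 dose of IMP (IMP is either FS eMDPI or Albuterol eMDPI for the DS group". The same sentence continues with the comparator and the second condition: "or SoC medication for the SoC group) and at least 1 postbaseline ACT assessment". So a dose condition is written for each arm, and the ACT condition is common to both.

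SAP 6.1 then states: "The mITT analysis sets will be used for all data analyses, unless otherwise specified". SAP 6.2.2 names mITT as the primary set. Neither sensitivity analysis in 6.2.3, nor the Week 12 supplementary analysis in 6.2.4, names a different one. The ITT set serves disposition and baseline summaries only.

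Four other places bear on who can fail the dose condition:
- Protocol 4.1, entry criterion c: "The patient is currently on treatment with a moderate- to high-dose ICS with LABA".
- Protocol 3.1, SoC arm: "Patients in the SoC group will be reimbursed or given a voucher to use to purchase their existing maintenance ICS with LABA".
- Protocol 3.1, DS arm: "Upon demonstrating competency, patients in the DS group will have their maintenance ICS with LABA switched to the FS eMDPI". Protocol Appendix B lists randomisation before the DS training at Visit 1.
- SAP 3.1.3, safety set: "all patients in the DS group who receive at least 1 dose of IMP and all patients in the SoC group".

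SAP 5.2 plans a disposition count of patients in the "ITT analysis set who did not use the inhaler". There is no matching count of SoC patients who did not take their medication.

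**The concern.** The trial asks whether the Digital System works better than usual care, and it is open-label. A condition that is met or failed after allocation is known, and that can realistically be failed in one arm only, breaks the comparison of groups as randomised.

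The plan's scoring rules make the gap visible. SAP 4.3 and 6.2.2 both count discontinuation for technology failure, or for disliking the platform or the IMP, as nonresponse. A patient who rejects the system before a first inhalation fits the intent of that rule but is outside the set to which it is applied. If such patients would mostly be nonresponders, leaving them out raises the DS response rate, and with it the chance of declaring success when the randomised arms do not differ.

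**Working it through.** **1. Can each arm fail the dose condition?**

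| | DS | SoC |
|---|---|---|
| Product counted as a dose | FS eMDPI or Albuterol eMDPI, new at Visit 1 | Existing medication, already in use at entry |
| Start depends on | Demonstrated competency, after randomisation | Nothing new |
| Dose test in the safety set | Yes | No |
| Non-use counted in disposition | Yes | No |
| How a first dose is verified | Inhaler log | Not stated |

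The SoC half of the condition exists but can hardly be failed.

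**2. Reproduce the design figures.** Inputs from SAP 2.4: 200 DS and 150 SoC patients; priors Beta(0.5, 0.5) for DS and Beta(9.52, 11.88) for SoC; success if the posterior probability that OR > 1 is at least 0.95. With x responders of n in DS and y of 150 in SoC, the posteriors are Beta(0.5 + x, 0.5 + n − x) and Beta(9.52 + y, 11.88 + 150 − y). The probability of success is the sum of the binomial probabilities over all (x, y) that meet the rule.
- 58% v 45%: 81.7% (plan: about 82%).
- 45% v 45%: 4.6% (plan: 1-sided 5%).
- Two-proportion power, 1-sided 5%: 78.0% (plan: 78%).

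This calculation leaves out baseline ACT and the center effect, which are in the SAP 6.2.2 model.

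**3. Drop k DS patients.** The true rate is 45% in both randomised arms, so 200 × 0.45 = 90 responders are expected in DS. If the k patients dropped respond at rate r, the DS rate in mITT is (90 − k·r)/(200 − k). For example, k = 2 and r = 0 gives 90/198 = 45.5%. The success rule is recomputed for n = 200 − k. The documents give no count of non-starters, so k is assumed, and each patient dropped is assumed to have a postbaseline ACT, so that the dose condition alone removes the patient.

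| k dropped | DS rate in mITT, r = 0 | Type 1 error, r = 0 | Type 1 error, r = 20% |
|---|---|---|---|
| 0 | 45.0% | 4.6% | 4.6% |
| 1 | 45.2% | 5.1% | 4.9% |
| 2 | 45.5% | 5.6% | 5.2% |
| 3 | 45.7% | 6.2% | 5.5% |
| 5 | 46.2% | 7.3% | 6.0% |
| 10 | 47.4% | 11.3% | 7.8% |

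At r = 45% the error stays between 4.6% and 4.7% for every k in the table.

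**The case against.** The strongest reply is that almost nobody will be removed. One inhalation from either device is enough. SAP 8.2 says the first dose is used for testing at the site on the day of randomisation. Willingness to switch is an inclusion criterion, and accepting the App terms is a condition of enrolment. A patient who abandons the inhaler after the site test stays in mITT if there is a postbaseline ACT. This stands, and it is why small counts are the relevant ones. It does not close the gap: SAP 8.2 itself provides for patients whose first dose is not used that day, and SAP 5.2 plans to count non-users.

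A second reply is that patients who are never switched would presumably stay on their previous ICS with LABA and respond much as SoC patients do. If so, dropping them does no material harm. The documents do not settle which response rate applies.

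A third is that the ACT condition removes many early leavers anyway, in both arms. That is true, and it means that deleting the dose condition alone would not bring those patients back. But Protocol 4.3 asks for the end-of-treatment assessments at early termination where possible, so a non-starter can have an ACT and be excluded on dose alone.

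Three stronger readings are tempting and are not supported:
- A reader might infer that the SoC arm has no dose condition. SAP 3.1.2 states one. That it cannot be failed in practice is an inference from how SoC treatment is supplied and recorded; medication and adherence questions do cover both arms, and the CRF is not available.
- A reader might infer that no rule covers a DS patient who does not start. Protocol 4.3 requires withdrawal for a request to stop the IMP, for noncompliance with eMDPI administration in the investigator's opinion, and for use of other SABA products; each could apply. A patient so withdrawn would still be outside mITT.
- A reader might infer that exclusion lowers the bar for success. With 68 of 150 SoC responders, DS needs 108/200 (54.0%), 105/195 (53.8%) or 103/190 (54.2%). The required rate stays near 54%; what changes is the rate in the patients who remain.

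**Conclusion.** The point holds in a limited form. The dose condition operates on DS alone in practice, acts after open-label randomisation, and takes undosed DS patients out of the primary and both sensitivity analyses without a score. If those patients would respond less often than the rest, the direction favours DS.

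The likely size is modest: a Type 1 error of 5.1% to 6.2% for 1 to 3 nonresponders dropped, against 4.6% with none and a stated 5%. It reaches 7.3% or 11.3% only with 5 or 10. Extending the calculation to 20 patients gives 24.0%, but that needs a tenth of the DS arm never to inhale once, all with a postbaseline ACT and all nonresponders; the site test dose makes that implausible. All of these figures rest on assumed counts, on 45% true response in both arms, and on the SAP 2.4 rule without covariates. The change is worth making because it is cheap and protects the main comparison.

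**What to change.** In SAP 3.1.2 and 6.2.2, analyse the primary endpoint in all randomised patients, as randomised, with the same scoring in both arms:
1. Patients who discontinue for a reason on the SAP 6.2.2 nonresponder list are nonresponders.
2. All others are scored on the Week 24 ACT or, failing that, the ET ACT.
3. Patients with neither are nonresponders.

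Step 3 must cover SoC as well. Scoring only DS non-starters as failures, while the ACT condition still removes SoC patients without an ACT, would create a bias against DS. The same step removes the conflict between the postbaseline ACT condition and SAP 4.3, which counts early discontinuers without an ET visit as failures.

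Keep the dose condition for the device-based, DS-only summaries, and list the change in SAP 11, which already records one revision of mITT.

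The cost is SAP wording, possible at any time before database lock. Response rates may fall slightly, mainly in DS if there are non-starters. For scale, if 4 of 200 DS patients never start and count as nonresponders while the rest respond at 58%, the DS rate is 196 × 0.58 / 200 = 56.8%. The probability of success against 45% in SoC is then 75.0%, compared with 81.4% when the 4 are dropped. With no non-starters, the dose part of the change has no effect.

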If the reason for withdrawal from the study or discontinuation from IMP is an adverse event and/or adverse device effect, monitoring will be continued as applicable (eg, until the event has resolved or stabilized, until the patient is referred to the care of a healthcare professional, or until a determination of a cause unrelated to the IMP or study procedure is made). The specific event or test result (including repeated test results, as applicable) must be recorded both on the source documentation and in the CRF; both the adverse events page and/or adverse device effect page and the termination page of the CRF will be completed at that time. The investigator must inform the contract research organization (CRO) as soon as possible of each patient who is being considered for withdrawal due to adverse events. Additional reports must be provided when requested.

If a patient is withdrawn from the study or discontinues IMP for multiple reasons that include adverse events, the relevant page of the CRF should indicate that the withdrawal was related to an adverse event. An exception to this requirement will be the occurrence of an adverse event that in the opinion of the investigator is not severe enough to warrant discontinuation but that requires the use of a prohibited medication, thereby requiring discontinuation of the patient. In such a case, the reason for discontinuation would be "need to take a prohibited medication," not the adverse event.

In the case of patients lost to follow-up, attempts to contact the patient must be made and documented in the patient's medical records and transcribed to the CRF.

All assessments should be performed according to the protocol for the end of treatment visit or upon early termination if possible. Patients are required to return the FS eMDPI and Albuterol eMDPI (used and unused) upon withdrawal from the study.

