6.1. Assessments of Patient-Reported Outcomes

6.1.1. Asthma Control Test

The ACT is a simple, patient-completed tool used for the assessment of overall asthma control. The 5 items included in the ACT assess daytime and nighttime asthma symptoms, use of rescue medication, and impact of asthma on daily functioning. Each item in the ACT is scored on a 5-point scale, with summation of all items providing scores ranging from 5 to 25. The scores span the continuum of poor control of asthma (score of 5) to complete control of asthma (score of 25), with a cutoff score of 19 and below indicating patients with poorly controlled asthma (Schatz et al 2006).

The ACT should be the 1st questionnaire completed by all patients during a study visit (followed by the Mini-AQLQ, WPAI questionnaire, BMQ, and then the BIPQ, respectively, all completed by patients 18 years of age or older, and should precede any discussion between the patient and investigational center personnel. The self-administered version of the ACT will be answered by the patients at Visit 1, Visit 2, Visit 3, or at the ET visit. For Visit 1, Visit 3, or the ET visit, the ACT will be administered in person at the investigational center. For Visit 2, the ACT may be administered by telephone. The investigators and personnel will be provided with detailed instructions for administering the ACT in order to achieve maximum compliance in a clinical study environment (or by telephone) and maximum data quality. Caregivers or investigational center personnel will not be allowed to interfere or communicate with the patient completing the questionnaire beyond restating the question(s) on the questionnaire exactly as they have been written. After completion of the ACT, investigational center personnel will check the questionnaires for completeness and legibility. Detailed instructions for administering, scoring, and analyzing the ACT are provided in the Statistical Analysis Plan.

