4.3. Handling Withdrawals and Missing Data

For the primary endpoint, patients who discontinue early due to technology failure, disliking the digital platform, disease worsening, adverse experience or disliking the IMP will be counted as treatment failures. For those who discontinue early not to these reasons, the ACT value assessed at ET visit will be used. Those who discontinue early and do not have an ET visit will be counted as treatment failures.

For the SUS items 1, 3, 5, 7, and 9, if response to 1 item is missing, the missing item will be replaced by the average of the remaining 4 responses. For items 2, 4, 6, 8, and 10, if response to 1 item is missing, the missing item will be replaced by the average of the remaining 4 responses. If response to 2 or more of items 1, 3, 5, 7, and 9 are missing, or 2 or more of items 2, 4, 6, 8, and 10 are missing, the overall SUS score will be set to missing.

For the BMQ subscales, if response to 1 item within a subscale is missing, the missing response will be replaced with the average of the remaining responses within the subscale. If response to 2 or more items within a subscale are missing, the missing responses will not be replaced and the subscale score will be set to missing.

For the BIPQ cognitive subscale, if response to 1 item within the subscale is missing, the missing response will be replaced with the average of the remaining responses within the subscale. If response to 2 or more items within the subscale is missing, the missing responses will not be replaced and the subscale score will be set to missing. For the emotional subscale, if 1 of the responses is missing then the subscale will be set to missing.

For an incomplete mini-AQLQ, the overall score for a particular visit will not be calculated if 1 or more responses are missing; total scores for the domains will be regarded as missing if 1 or more item will be incomplete.

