6.2.2. Primary Analysis

To analyze the primary variable, the following estimand framework will be used:

1. Population: The patients met all of the inclusion criteria and none of the exclusion criteria. The mITT analysis set will be the primary analysis set for the primary endpoint.
2. Variable: The primary endpoint will be a binary response variable at Week 24. A patient will be defined as a responder if the patient achieves an ACT score of greater than or equal to 20 or an increase of greater than or equal to 3 ACT units from baseline to Week 24. Otherwise, the patient will be defined as a nonresponder.
3. Intercurrent events: Treatment discontinuation due to an adverse event, lack of efficacy, technology failure, disliking the DS, disliking IMP, or other reasons. For those who discontinue the treatment before Week 24, no further data will be collected.
4. Population-level summary: The primary endpoint will be analyzed using a logistic model, where binary variable responder rate (Yes/No) will be modeled through logit link function, with baseline ACT score and treatment as explanatory factors. For those who discontinue the treatment before Week 24 due to technology failure, disliking the digital platform, adverse event related to IMP, or disliking the IMP, the patients will be defined as nonresponders; for those who discontinue early not due to these reasons, the response

at the ET visit will be used. The mean and 95% credible intervals of the response rates and OR from the posterior distributions will be calculated and presented. An informative prior will be assumed for the model coefficient for treatment and non-informative priors will be assumed for all other model coefficients.

Logistic regression model allowing for different response rates at enrolling investigational centers will be used for testing the hypothesis $H_0: \beta_1 = 0, H_1: \beta_1 > 0$ in the following model:

$$\ln\left(\frac{p_{ij}}{1-p_{ij}}\right) = \beta_0 + \beta_1 x_i + \beta_2 \text{baseline ACT value} + \text{Center}_j$$

where x_i = treatment group i , p_{ij} = response proportion of treatment group i at Center j, Center_j = random center effect of center j.

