6.2.3. Sensitivity Analyses

Sensitivity analysis 1: This analysis will be performed by imputing missing ACT values using the multiple imputation (MI) method assuming missing at random (MAR). Those who discontinue the treatment before Week 24 due to technology failure, disliking the digital platform, adverse event related to IMP, or disliking the IMP will be considered having missing data. For those who discontinue early not due to these reasons, the ACT value assessed at the ET visit will be used. Those who discontinue early and do not have an ET visit will be considered having missing data.

The following steps will be performed for the analysis:

- Create complete datasets using imputation. The SAS code is as follows:

```
proc mi data = yy out = yy2 seed = 4192 n impute = 500 minimum = 5 maximum = 25;  
  class trt;  
  var trt actbase v2 v3;  
  monotone regpmm;  
run;
```
- For each dataset, the clinically important improvement in asthma control variable will be derived for each patient as defined in Section 6.2.1.
- Analyze each dataset using the model described below for the primary endpoint.

```
ods output Diffs = dif LSMeans = lsm;  
proc genmod data = indata;  
  by visit_imputation_;  
  class trt;  
  model y = trt actbase / dist = binomial;  
  lsmeans trt/pdiff cl diff exp;  
run;  
ods output close;
```

- The output datasets from the above analysis will contain odds ratio estimates from each of the 500 datasets. An overall estimate will be generated using PROC MIANALYZE . The SAS code is as following:

```
proc mianalyze data=zz;
  by visit;
  modeleffects estimate;
  stderr stderr;
  ods output paramestimates=or;
run;
```

Sensitivity analysis 2: The primary variable will be analyzed using the same method as defined in Section 6.2.2 excluding the random site effect from the logistic model. The SAS code will be used for the analysis:

```
proc mcmc data = x nbi = 1000 nmc = 500000 thin = 20 seed = 159 outpost =
post2 monitor = (beta0-beta2 sigma2 pi pi0 pooled or) statistics=(summary
intervals);

parms beta0-beta2 0;
prior beta0 ~ normal (mean = -0.231, var = 0.192);
prior beta1 ~ normal (mean = 0.236, var = 9.912);
prior beta2 ~ normal (mean = 0, var = 1000);
eta = beta0 + beta1*trt + beta2*y0;
pi = logistic(eta);
pi0 = logistic(beta0 + beta2*y0);
model count ~ binomial(n = total, p = pi);
pooled = exp(beta1);

run;
```

where count = number of responders and total = number of patients.

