8.2. Duration of Exposure to IMP

Since the dosing of the test IMP is on an as-needed basis, there is no set maximum exposure.

Duration of exposure to IMP is the number of days from date of the 2nd dose (since the 1st dose is used for testing at the study site on date of randomization) to date of last dose of IMP (last dose of IMP date – 2nd dose of IMP date + 1). If the 1st dose is not used on date of randomization, the duration of exposure to IMP will be calculated as last dose of IMP date – 1st dose of IMP date + 1 assuming no testing is done at study site for the patient. Number and percent of patients will be summarized by duration of exposure to IMP categories \leq 1 week, >1 to \leq 2 weeks, ..., >23 to \leq 24 weeks, and > week 24. Duration of exposure to IMP (days) and number of inhalations will also be summarized as continuous data using descriptive statistics.

The number of days a patient takes IMP will be summarized as continuous data using descriptive statistics. If a patient takes more than 1 IMP treatment on the same day, the patient will be counted only once in the summary; if a patient does not take any IMP treatment on a given day the patient will be counted as zero on that day. Summaries will be presented separately for FS eMDPI and Albuterol eMDPI.

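### Patients who leave before Week 12 without an early-termination ACT drop out of the primary analysis set, although SAP 4.3 counts early leavers with no ET visit as treatment failures

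*SAP*

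**What the plan says.** SAP 3.1.2 defines the mITT set by two conditions, at least one dose and a post-baseline ACT: "SoC medication for the SoC group) and at least 1 postbaseline ACT assessment". SAP 6.2.2 makes this the primary analysis set, and SAP 6.1 extends it: "The mITT analysis sets will be used for all data analyses, unless otherwise specified".

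Two rules in the SAP turn early leavers into failures:

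- SAP 4.3, for the primary endpoint: "Those who discontinue early and do not have an ET visit will be counted as treatment failures".
- SAP 6.2.2, on certain reasons for stopping treatment early: "due to technology failure, disliking the digital platform, adverse event related to IMP, or disliking the IMP, the patients will be defined as nonresponders".

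Neither rule says that it applies only within mITT.

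On when the ACT is obtained, Protocol 6.1.1 states: "The self-administered version of the ACT will be answered by the patients at Visit 1, Visit 2, Visit 3, or at the ET visit". Protocol Table 5 puts Visit 2 at Week 12. For patients who withdraw, Protocol 4.3 states: "All assessments should be performed according to the protocol for the end of treatment visit or upon early termination if possible". SAP 6.2.2 adds that no data are collected after discontinuation.

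Protocol 9.2.2 had required only a post-baseline assessment on any study endpoint. SAP 11 discloses the change to an ACT, but not how the new condition interacts with SAP 4.3.

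**The concern.** The entry condition removes patients whom the failure rules appear written to count. Someone who gives up on the App at Week 4 and does not attend an ET visit leaves the analysis. Someone who gives up for the same reason at Week 14, after a Week 12 ACT, is a nonresponder. The only difference is whether an ACT was recorded first.

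The condition applies to both arms, so the direction of any bias depends on which arm loses more patients early. Greater loss in DS is plausible: the trial is open-label, only DS patients change inhaler and adopt an App, and technology failure or dislike of the DS can arise only there. The documents do not show that it happens. If DS loses more, the mITT result overstates DS effectiveness; if SoC loses more, it understates it.

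**Working it through.** **Who is dropped.** The table follows the text for a patient who has had a dose, leaves early, and has no ACT outside the scheduled visits.

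| Week 12 ACT | At early termination | In mITT? | Treatment in the primary analysis |
|---|---|---|---|
| Yes | No ET visit | Yes | Failure (SAP 4.3) |
| No | ET visit with ACT | Yes | ET response, or failure if the reason is listed |
| No | No ET visit | No | Absent, though SAP 4.3 says failure |
| No | ET visit without ACT | No | Absent; SAP 4.3 has no specific rule unless the reason is listed |

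The third row is the conflict. It also covers a patient who misses the Week 12 ACT and leaves later with no ET visit.

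**Whether another analysis restores them.** Sensitivity analysis 1 (SAP 6.2.3) says "Those who discontinue early and do not have an ET visit will be considered having missing data" and imputes, but names no analysis set, so SAP 6.1 keeps it within mITT. Sensitivity analysis 2 only removes the site effect. The ITT set is used for disposition and baseline summaries.

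**Size: inputs.** From SAP 2.4: priors Beta(0.5, 0.5) for DS and Beta(9.52, 11.88) for SoC; success if the posterior probability that OR > 1 is at least 0.95; response 58% and 45%; 200 and 150 analysed; 388 enrolled. Splitting 388 in the ratio 4:3 gives 388 × 4/7 ≈ 222 and 388 × 3/7 ≈ 166. The loss fractions e1 (DS) and e0 (SoC), meaning patients with no post-baseline ACT, are assumptions; the documents give only 10% early dropout overall.

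**Check on the method.** Exact enumeration over both binomials at 200/150 and 58%/45% gives a success probability of 0.817, against about 82% in the SAP.

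**No true difference.** Let response among all randomised patients be 45% in both arms, with patients who have no ACT counted as failures. In mITT the rates become 0.45/(1 − e1) and 0.45/(1 − e0), on 222(1 − e1) and 166(1 − e0) patients. At 10%/2% these are 0.45/0.90 = 50.0% on 200 patients and 0.45/0.98 = 45.9% on 163.

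| Loss DS/SoC | Chance of declaring DS better in mITT |
|---|---|
| None (all randomised) | 4.7% |
| 2%/2% | 4.9% |
| 5%/5% | 5.2% |
| 10%/10% | 6.0% |
| 5%/2% | 8.7% |
| 10%/5% | 13.7% |
| 10%/2% | 20.3% |
| 2%/5% | 2.8% |

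**Planned difference present in mITT (58% vs 45%).** The all-randomised difference is 0.58(1 − e1) − 0.45(1 − e0). At 5%/2% it is 0.551 − 0.441 = 0.110.

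| Loss DS/SoC | Difference, all randomised (13.0 points in mITT) | Power in mITT | Power, all randomised |
|---|---|---|---|
| 5%/5% | 12.35 points | 83.3% | 80.0% |
| 5%/2% | 11.0 points | 83.8% | 72.3% |
| 10%/2% | 8.1 points | 83.0% | 49.5% |
| 2%/5% | 14.1 points | 84.0% | 88.6% |

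These figures use the sample-size rule. Baseline ACT and the random centre effect of SAP 6.2.2 are not modelled.

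**The case against.** The sponsor can fairly say that SAP 4.3 is a data-handling rule for use inside the set named in SAP 6.2.2. It is not empty there, because it still governs patients with a Week 12 ACT who leave later. The narrower mITT is declared in SAP 11, and the sample size already allows for non-evaluable dropouts. That reading is possible, but SAP 4.3 does not state it, so the text needs a sentence either way.

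The affected group may be small. Leavers who give an ET ACT stay in mITT, and Protocol Appendix E requires repeated contact attempts. An ACT taken at a Clinically Driven Assessment could keep a patient in, though none is scheduled. The dose condition should remove few DS patients, "since the 1st dose is used for testing at the study site on date of randomization" (SAP 8.2), although nothing shows that this covers SoC. Not using the App does not in itself exclude anyone.

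The larger error rates also need unequal loss. At 3%/2% the chance of a false success is only 5.9%. The 10%/2% case needs about 22 + 3 = 25 patients with no post-baseline ACT, roughly two-thirds of the 388 − 350 = 38 planned dropouts, and should be read as extreme. All this stands as a limit on size.

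Finally, SAP 5.1 and 5.2 already plan counts for each analysis set and withdrawal reasons, which should make unequal exclusion visible if tabulated by arm. They would not show its effect on the estimate.

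**Conclusion.** The concern holds. The primary set omits patients whom SAP 4.3, as worded, counts as failures, and no planned responder analysis includes them. This follows from the text and needs no figure.

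The size is conditional. With equal loss in the two arms the effect on false success is slight. With greater DS loss it can approach double the 4.7% reference (8.7% at 5%/2%) or exceed it several-fold in the extreme case; with greater SoC loss the rule becomes conservative. These rates are errors relative to an estimand in which early leavers without an ACT are failures, which is the position SAP 4.3 takes. Neither the amount of early loss nor its direction is known from the documents.

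**What to change.** - In SAP 3.1.2 and 6.2.2, run the primary responder analysis on all randomised patients, as randomised.
- In SAP 4.3, state that any patient with no post-baseline ACT is a nonresponder, whether or not an ET visit took place.
- Keep the present mITT analysis as a sensitivity analysis, and state in SAP 5.2 that the number it excludes is tabulated by arm.
- Add the change to SAP 11.

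A lighter route is to say that SAP 4.3 applies only within mITT and add an all-randomised nonresponder analysis as a sensitivity analysis. That exposes the problem but leaves the primary result resting on the restricted set.

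The cost is SAP wording before database lock and one extra run on data already held. Response rates fall somewhat in both arms. The power given up is about 3 points at 5%/5% loss (83.3% to 80.0%) and more if DS loses more patients, down to 49.5% at 10%/2%. That larger fall reflects failures which the mITT set would have left out.
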